7) In 2021, Khanagar *et al.*,^[18] published a systematic review aiming to document the scope and performance of the artificial intelligence-based models that have been widely used in orthodontic diagnosis, treatment planning, and predicting the prognosis. Artificial Intelligence (AI) technology has been widely applied for identifying cephalometric landmarks, determining need for orthodontic extractions, determining the degree of maturation of the cervical vertebra, predicting the facial attractiveness after orthognathic surgery, predicting the need for orthodontic treatment, and

orthodontic treatment planning. Most of these artificial intelligence models are based on either artificial neural networks (ANNs) or convolutional neural networks (CNNs). These systems can simplify the tasks and provide results in quick time which can save the dentist time and help the dentist to perform his duties more efficiently. These systems can be of great value in orthodontics.

Anchorage planning is fundamental factor for success of treatment specially when extraction decision was made. Many studies and textbooks discussed in details anchorage.

- In 2019, Li *et al.*^[22] Discussed the factors related to decision making of Anchorage which were:

- 1- Curve of spee
- 2- Nasolabial Angle
- 3- UL- EP

- In 2016, Mandava, Ganugapanta and Pradess^[24], published a literature review entitled “Anchorage in Orthodontics” in which anchorage was discussed in details regarding;

- Different Anchorage definitions according to Nanda and Proffit.
- Different Anchorage Classifications according to Manner, Number of anchor units, Marcottee’s Classification 1990 (*Group A, B, C*), Gianelly and Goldman 1971 (*Maximum, Moderate, Minimum Anchorage*).
- Sources of Anchorage Intraoral sources as Alveolar Bone, Teeth, Basal Bone, Cortical Bone, Musculature,
- Anchorage planning depends on the anchorage requirements:

1- Number of teeth to be moved

2- Type of teeth being moved

3- Type of tooth movement

4- Periodontal condition

5- Duration of tooth movement

6- Anchorage value: Anchorage value of any tooth is equal to its root surface area. Molar and 2nd premolar in each arch is approximately equal in surface area to incisors and canine

- In 2019, Nahidh, Am and Sc [30], published Understanding Anchorage in Orthodontics a Review Article in which different anchorage classifications were discussed in full details as:

I. According to the manner of force application:

1. Simple anchorage

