- Patients with decreased vertical dimension and forward growth rotation of the mandible due to their strong musculature show space loss and anchorage loss at slower rate.

- **Nanda, 2012 [31] in Biomechanics and Esthetics Strategies in Clinical Orthodontics book Chapter 10 (Biomechanic Basis of Extraction Space Closure) classified anchorage into 3 different groups summarized as the following:**

Group A	Group B	Group C
Posterior Segment Maintained in Position (75% of extraction space is needed for anterior retraction)	Symmetric space closure 50% - 50% ↓ Least difficult	Non-critical Anchorage 75% of space closure by movement of the posterior

In which Determinants of Space Closure are:

- 1- Amount of Crowding
- 2- Anchorage
- 3- Axial Inclination of canines and incisors
- 4- Midline discrepancies, left and right symmetry
- 5- Vertical dimension

- **(William R. Proffit, 2018) [44] in his book Contemporary Orthodontics Chapter 16**
Maximum Incisor retraction requires maximum anchorage control, the same basic approach is needed with any appliance when maximum anchorage is needed: increased reinforcement of posterior anchorage and decreased strain on that anchorage.
- 1- Reinforcement by lingual arch

2- Two-Step Frictionless Retraction: Individualized retraction of the canines with auxiliary springs before a second stage of incisor retraction with closing loops is an attractive method for reducing the strain on posterior anchorage

Retraction With Skeletal Anchorage

3- Skeletal anchorage for retraction of protruding incisors is the only way to close extraction spaces totally by retracting the incisor–canine arch segment. The major advantage of skeletal anchorage in retraction of the anterior segment is that it offers vertical as well as anteroposterior control of the teeth to create the desired display of the incisors.

The major disadvantage of skeletal anchorage for maximum incisor retraction in either arch is that it makes over-retraction of the incisor segments possible. The treatment objective is to improve the patient's dentofacial appearance and decrease social problems related to it.

Retracting the anterior teeth too much makes the patient look worse, not better, as lip support is decreased and the nasolabial fold is accentuated. This is more of a problem in Class II or Class III camouflage than correction of bimaxillary protrusion.

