Other applications of skeletal anchorage, including distal movement of the entire dental arch to reduce incisor protrusion.

Skeletal anchorage, created by placing bone screws in either arch in the canine region, is the easiest and most effective way to close an extraction space by bringing posterior teeth forward. This is particularly advantageous when more forward movement is needed on one side than the other. In both minimum and maximum retraction, temporary anchorage devices (TADs) now make it much easier to handle what previously were very difficult situations.

7. Study objectives and hypotheses:

The aim of the study includes hypothesis

The program decisions will meet the decisions of the orthodontist in well finished cases in terms of extraction decision and anchorage planning

Objectives:

- To study the efficiency of the program decisions in terms of extraction/non-extraction
- Anchorage planning decisions

III. Methods:

A) Trial design

8. Data and records of previously treated patients at Cairo university and Future University will be collected from the archive before the index test is performed so that the decision support system will be constructed based on the given data

B) Participants:**9. Eligibility criteria:****Inclusion Criteria:**

- 1- Cases with well finished orthodontic treatment.
- 2- Cases with history of crowding more than 10 mm and requiring extraction.
- 3- Cases with no severe skeletal discrepancy.
- 4- Well documented cases with both pre-operative and post-operative records.
- 5- Patients with a full set of permanent teeth erupted

Exclusion Criteria:

- 1- Improperly finished orthodontic cases.
- 2- Cases with mild crowding managed by treatment options other than extraction.
- 3- Growing patients or showing any residual growth remaining in cephalometric analysis
- 4- Cases with severe skeletal discrepancy.
- 5- Poorly documented cases.
- 6- Patients not sticking to anchorage plan

10. On what basis potentially eligible participants will be identified:

Recruiting well finished cases having history of crowding from Kasr el Ainy with no severe skeletal discrepancy, cases should be well documented. The precise and complete documentation of the patients in terms of the presence of:

- (1) Preoperative and postoperative x-rays.
- (2) Good quality preoperative and postoperative photographs.
- (3) Preoperative and postoperative study models.

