Statistical analyses will be performed using SPSS (version 22.0; IBM Corp, Armonk, NY). More than 1 type of statistical analysis will be used to address the outcomes. Cohen's kappa coefficient will be used to measure the agreement between the 2 methods on the basis of choice of the same options without consideration of the value assigned to each option (qualitative data). If a value were assigned to the option, it would be given 1, and if it were not assigned, it would be given 0. Cohen's kappa coefficient is a more robust method than simple percentage agreement, and its value dictates the strength of agreement (<0.20, poor; 0.21-0.40, fair; 0.41-0.60, moderate; 0.61-0.80, good; and 0.81-1.00, very good).

The concordance correlation coefficient would be used to measure the agreement between the 2 methods on the basis of the values (%) assigned for each treatment option by the 2 methods (quantitative data).

A value of ≥ 1 , corresponds to perfect agreement; ≥ 0.8 , very good; ≥ 0.7 , good; ≥ 0.5 , moderate, ≥ 0.4 , fair; ≥ 0.3 , poor; and 0, no agreement.

The sum of absolute difference and the relative sum of absolute difference were used to measure the percent error between the 2 methods on the basis of the values assigned for each treatment option (quantitative data).

18. How indeterminate index test or reference standard results will be handled:

It is not applicable as the outcome will be based on decisions made by the program

19. How missing data on the index test and reference standard will be handled

Any Patient file with incomplete data will not be included from the beginning in the study

20. Sample size calculation and how it was determined

Sample size is being calculated and waiting for approval

IV. Ethics and dissemination**21. Research ethics approval**

This protocol will be reviewed by the Ethics Committee of Scientific Research –Faculty of Oral and Dental Medicine Cairo University

22. Protocol amendments

Any modification to the protocol which may have an impact on the conduct of the study, potential benefit of the patient or may affect patient safety will require a formal amendment to the protocol. Such amendment will be agreed upon by the Council of orthodontic Department.

23. Informed consent

Template will be reviewed by the Ethical committee and will be signed by the patients or their legal guardians

24. Confidentiality

All study-related information will be stored securely by the personnel conducting the study

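### If anchorage is recorded on an ordered demand scale, one overall unweighted kappa scores a one-step difference and a maximum-versus-minimum reversal alike; a weighted kappa beside it would separate them

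*Protocol*

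**What the plan says.** Section 7 of the protocol sets two objectives, the extraction/non-extraction decision and "Anchorage planning decisions". Section 17 does not assign separate statistics to them. For categorical agreement it names one measure, Cohen's kappa, taken "on the basis of choice of the same options without consideration of the value assigned to each option". The data are treated as qualitative, and the coding is binary per option: "If a value were assigned to the option, it would be given 1, and if it were not assigned, it would be given 0". The size of kappa is then read against verbal bands: "<0.20, poor; 0.21-0.40, fair; 0.41-0.60, moderate; 0.61-0.80, good; and 0.81-1.00, very good". No weighting is mentioned.

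Section 17 also plans a concordance correlation coefficient, a sum of absolute differences and its relative form. All three work on the percentage that each method gives to each treatment option.

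The Methods do not name the anchorage classes from which the program and the clinicians choose. Classes appear only in the literature review in section 6. The demand-based ones include "Maximum, Moderate, Minimum Anchorage", the same three levels labelled Type A, B and C, and Groups A, B and C. Group A is described by "75% of extraction space is needed for anterior retraction", Group B by an even split, and Group C by three quarters of the closure coming from the posterior segment. The Type A/B/C list has a fourth entry, absolute anchorage, without a stated rank. The same review lists schemes with no order, such as those by manner of force application, jaws involved or site.

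**The concern.** Unweighted kappa counts a pair of decisions as the same or different and nothing more. For a yes/no extraction decision nothing is lost. On an ordered scale of anchorage demand, the distance between two choices carries information: on the Group A/B/C description, choosing A against C reverses which segment takes most of the space, and choosing A against B does not.

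If the anchorage objective is summarised by one overall kappa, a program that is always within one class of the clinician and a program that swaps the two extremes can receive the same figure and the same verbal label. A reader of the result would want to know which of the two was observed.

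**Working it through.** The protocol gives no sample size, expected agreement or target kappa, so there is no stated figure to reproduce. The tables below are assumptions chosen to isolate the effect: equal margins and equal exact agreement, with only the distance of the errors changed.

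**Inputs.** Three ordered classes (maximum, moderate, minimum) taken from section 6; 100 cases; margins 30/40/30 for both methods; 68 exact matches and 32 disagreements.

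- Table X, all errors one step: rows [22, 8, 0], [8, 24, 8], [0, 8, 22].
- Table Y, all errors maximum-versus-minimum: rows [14, 0, 16], [0, 40, 0], [16, 0, 14].

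**Formula.** Kappa = 1 − (weighted observed disagreement) / (weighted disagreement expected from the margins). The disagreement weights for one step and two steps are 1 and 1 (unweighted), 0.5 and 1 (linear), 0.25 and 1 (quadratic).

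**Expected disagreement, the same for both tables.** One-step cells: 4 × 0.12 = 0.48. Two-step cells: 2 × 0.09 = 0.18.

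- Unweighted: 0.48 + 0.18 = 0.66
- Linear: 0.5 × 0.48 + 0.18 = 0.42
- Quadratic: 0.25 × 0.48 + 0.18 = 0.30

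**Results.**

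| Statistic | Table X (one step) | Table Y (reversal) |
|---|---|---|
| Unweighted | 1 − 0.32/0.66 = 0.515 | 1 − 0.32/0.66 = 0.515 |
| Linear | 1 − 0.16/0.42 = 0.619 | 1 − 0.32/0.42 = 0.238 |
| Quadratic | 1 − 0.08/0.30 = 0.733 | 1 − 0.32/0.30 = −0.067 |

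On the protocol's bands the unweighted value is moderate for both tables. The linear-weighted value is good for X and fair for Y.

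**Kappa under the 0/1 coding, options pooled.** There are 300 option indicators, and each discordant case makes two of them differ, so 64 differ. Observed agreement is 236/300 = 0.787. Each method marks one option in three, so chance agreement is 1/9 + 4/9 = 0.556. Pooled kappa is (0.787 − 0.556)/(1 − 0.556) = 0.52 for both tables.

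**Kappa under the 0/1 coding, each option separately.**

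- Table X: maximum (0.84 − 0.58)/0.42 = 0.62; moderate (0.68 − 0.52)/0.48 = 0.33; minimum 0.62.
- Table Y: maximum (0.68 − 0.58)/0.42 = 0.24; moderate 1.00; minimum 0.24.

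Reported this way, the two patterns do differ.

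**The other planned measures, each method putting 100% on one class.** The concordance correlation of the option values is 0.52 in both tables. Each discordant case contributes 200 points to the sum of absolute differences, so the total is 32 × 200 = 6400 in both.

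**The same measures with graded percentages (assumed).** Against 60/30/10 over maximum/moderate/minimum, a plan of 30/60/10 differs by 30 + 30 + 0 = 60 points, and a plan of 10/30/60 differs by 50 + 0 + 50 = 100. Distance then registers.

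**A second, milder set of tables.** With 90 cases, margins 30/30/30 and 18 disagreements (20%), unweighted kappa is 0.70 whether all errors are one step or all are reversals. Linear weights give 0.775 and 0.55; quadratic weights give 0.85 and 0.40. With the same proportions the values do not depend on the number of cases.

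**The case against.** The strongest reply is that the plan may already show the difference. The 0/1 coding can be read as giving one kappa per option, and those kappas separate the two tables. Section 17 also announces more than one type of analysis, and its percentage-based measures respond to distance when percentages are graded. Both points stand. A reader might infer that the study cannot tell near misses from reversals; the protocol does not support that. It is true only of a single overall or pooled kappa, with all-or-nothing percentages. Section 17 does not say whether options are pooled or how the percentages are formed.

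A reader might also take the quoted clause about disregarding the value as a decision to disregard anchorage order. It is not: the value there is the percentage given to an option, which the later measures handle. The point rests on the absence of weights and on the 0/1 coding.

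Nor can it be said that the study's anchorage scale is ordinal. The Methods name none, the background includes unordered schemes, and absolute anchorage has no stated rank. The point is therefore conditional on the scale chosen.

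Finally, unweighted kappa is a legitimate measure of whether the same decision was reached, which is how section 7 words the hypothesis, and weights are often left to an analysis plan, which is not at hand. That removes the charge of error. It does not remove the benefit of a weighted statistic on an ordered scale.

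**Conclusion.** The point holds as a low-cost improvement. If anchorage is recorded on one of the ordered demand scales in the background and summarised by one overall or pooled kappa, that figure gives a one-step difference and a maximum-versus-minimum reversal equal weight. In the main illustration the unweighted value is 0.52 for both patterns, against linear-weighted values of 0.62 and 0.24, which is two bands apart on the protocol's own labels.

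The size rests on assumed tables. These are extremes, since each contains only one kind of error; real data would mix the two and the gap would be smaller. Identical unweighted scores also require equal margins, because chance agreement changes with them. The exact figures should not be read as predictions for this study.

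**What to change.** In section 17:

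- Name the anchorage classes and their order, stating where absolute anchorage sits or that it is not used.
- Keep unweighted kappa for extraction/non-extraction.
- For anchorage, report a linear-weighted kappa with weights fixed before the analysis, together with the unweighted kappa and the full cross-table of program against clinician.

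This takes a few sentences and a standard calculation on the same data, with no extra patients. Defining the classes is the real work, because weights cannot be set without an order. The downside is that the weights are a convention and weighted values are not directly comparable with unweighted ones. The strength bands should be applied to each with that caveat.

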- (4) Detailed documentation of the treatment sequence and mechanics. If there were incomplete data provided in the patient's file; the patient will then be excluded from the study.

11. Where and when potentially eligible participants will be identified (setting,

location and dates)

Recruiting patients from Ksar El Ainy – Cairo University, future university archive with their specific eligibility criteria once the paper work is approved

12. Whether participants formed a consecutive, random or convenience series:

Any Patient that passes the inclusion criteria in terms of file including patient full records, Mechanics used were well registered and the case was well finished based on that the patient will be enrolled.

No subdivisions will be done

C) Test method:**13. Index test & reference standard in sufficient detail to allow replication**

A- The Preanalytical Phase:

Patients should have finished their orthodontic department at Cairo University with full Records available

B- The Analytical Phase:

Experts will analyze the outcome resulting from decision support system regarding extraction or non-extraction and anchorage planning and whether it is comparable to those conventional decisions reached by the orthodontic clinicians during treatment planning

C- Postanalytical Phase: Calculation of the efficiency of the system

14. Rationale for choosing the reference standard

Conventional Decisions (Decisions made by Orthodontic Clinicians) concerning extraction or non-extraction and anchorage planning for well finished cases

15. Definition and rationale for test positivity cut-offs of the index test & reference standard:

The study will test the efficiency of the decision support system according to those by the Orthodontic Clinicians

16 a. Clinical information and reference standard results will be available to the performers of the index test

Index test performers will be blinded

16 b. Clinical information and index test results will be available to the assessors of the reference standard

The assessors will be blinded from the treatment mechanics and results

D) Statistical analysis

17. Methods for estimating or comparing measures of diagnostic accuracy

Co-relation analysis will be used to compare the outcomes of both methods (conventional & computerized)

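### The kappa coding counts any option given a percentage as chosen, so if a method values several options in a case, kappa shows overlap of options and not whether the decisions match

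*Protocol*

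**What the plan says.** The hypothesis in item 7 is stated in terms of decisions: "The program decisions will meet the decisions of the orthodontist in well finished cases in terms of extraction decision and anchorage planning". The analytical phase in item 13 asks the same of the system's output, namely "whether it is comparable to those conventional decisions reached by the orthodontic clinicians during treatment planning".

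Item 17 measures agreement with three kinds of statistic.

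- **Cohen's kappa** is applied "on the basis of choice of the same options without consideration of the value assigned to each option". The coding is: "If a value were assigned to the option, it would be given 1, and if it were not assigned, it would be given 0". The result is read against fixed bands, since "its value dictates the strength of agreement".
- **A concordance correlation coefficient** uses the "values (%) assigned for each treatment option by the 2 methods (quantitative data").
- **Sums of absolute differences**, plain and relative, use the same percentages.

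Item 15, on cut-offs, only restates the aim. Item 18, on indeterminate results, says: "It is not applicable as the outcome will be based on decisions made by the program". Neither says how a decision is read from the percentages, and neither says what a percentage expresses. Elsewhere, the anchorage part of the literature review uses percentages for shares of space closure ("75% of extraction space is needed for anterior retraction"), which is not a strength of preference.

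**The concern.** The coding discards the one feature of the percentages that identifies a decision, namely which option is preferred. A program that puts 80% on the clinician's option and 20% on another gets the same 0/1 codes as one that puts 20% and 80%. In every case where a method values more than one option, kappa records that options overlap and says nothing about which was chosen.

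The bands then attach a verbal grade to that number, and the grade will be read as the answer to the hypothesis. The rule is written in the protocol, so this is not a detail left open for an analysis plan. Whether it does harm depends on how often a method values several options in one case, and the protocol does not say.

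**Working it through.** The protocol gives no sample size, expected kappa or frequency of multiple valued options, so it has no figure to reproduce. The inputs below are assumptions.

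**Set-up (anchorage).** Three unordered options and 90 cases, with the clinicians choosing each option in 30. Clinicians value one option per case. The program values only the clinician's option in 90 − s cases. In s split cases, balanced over the options, it values the clinician's option and one other. In w of the s split cases its highest-valued option is not the clinician's.

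Kappa = (Po − Pe)/(1 − Pe), where Po is observed and Pe is chance agreement.

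**Kappa under the protocol's coding, s = 36.** For each option the clinicians have 30 ones and the program has 30 + 12 = 42. The two codes differ in 12 cases.

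- Po = 78/90 = 0.867
- Pe = (30/90)(42/90) + (60/90)(48/90) = 0.511
- kappa = (0.867 − 0.511)/(1 − 0.511) = 0.73

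The protocol does not fix the unit for kappa. Pooling all case-by-option cells gives the same 0.73 here. The quantity w does not appear in the calculation.

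**Kappa on one decision per case (highest-valued option).** Po = 1 − w/90 and Pe = 1/3, so kappa = 1 − w/60.

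| w of 36 wrong | Decisions matching | Decision kappa | Coded kappa |
|---|---|---|---|
| 0 | 90/90 | 1.00 | 0.73 |
| 9 | 81/90 | 0.85 | 0.73 |
| 18 | 72/90 | 0.70 | 0.73 |
| 27 | 63/90 | 0.55 | 0.73 |
| 36 | 54/90 | 0.40 | 0.73 |

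On the protocol's bands the coded result is *good* throughout. The decision result runs from *very good* to *fair*.

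**Range over s.** The coded kappa is (360 − 2s)/(360 + s). The decision kappa runs from 1.00 down to 1 − s/60. The two are equal at w = 180s/(360 + s).

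| s | Coded kappa | Decision kappa, w = 0 to w = s | Equal at w |
|---|---|---|---|
| 0 | 1.00 | 1.00 | n/a |
| 9 | 0.93 | 1.00 to 0.85 | 4.4 of 9 |
| 18 | 0.86 | 1.00 to 0.70 | 8.6 of 18 |
| 36 | 0.73 | 1.00 to 0.40 | 16.4 of 36 |
| 90 | 0.40 | 1.00 to −0.50 | 36 of 90 |

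Below the point of equality the coding understates agreement, and above it the coding overstates it. Equality lies between 40% and 49% wrong, just under a coin toss.

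**Harmless case.** If each method values exactly one option and decisions match in 80% of cases, both kappas are 0.70.

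**Does the concordance coefficient fill the gap?** Take proportions over the 270 case-by-option cells, with s = 36. Let p be the program's larger value in a split case. Both means are 1/3, so the coefficient is 2·cov/(var of clinician + var of program), and the clinician variance is 1/3 − 1/9 = 0.2222.

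- p = 0.60, w = 0: cov = (54 + 36×0.60)/270 − 1/9 = 0.1689. Program variance = (54 + 36×0.52)/270 − 1/9 = 0.1582. Coefficient = 0.3378/0.3804 = 0.89.
- p = 0.95, w = 7: cov = (54 + 29×0.95 + 7×0.05)/270 − 1/9 = 0.1922. Program variance = (54 + 36×0.905)/270 − 1/9 = 0.2096. Coefficient = 0.3844/0.4318 = 0.89.

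The coefficient does respond to wrong decisions: at p = 0.95 it falls from 0.998 (w = 0) to 0.44 (w = 36). But the same value of 0.89 arises with no decision wrong and with seven wrong, so it cannot report how often decisions match.

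**Extraction.** Inclusion criterion 2 admits cases that required extraction, so the clinicians' extraction decision may be constant or nearly so. With 100 cases, all clinician decisions extraction and 90% agreement, Po = 0.90 and Pe = 1×0.90 + 0×0.10 = 0.90, so kappa = 0. At 100% agreement Pe = 1 and kappa is undefined. With clinicians 95/5 and 10 extraction cases called wrongly, Po = 0.90, Pe = 0.95×0.85 + 0.05×0.15 = 0.815 and kappa = 0.085/0.185 = 0.46. For this decision, kappa is therefore a poor summary even when computed on the right variable.

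**The case against.** **The trigger is not stated.** Clinician decisions come from completed, archived treatments, which suggests one option per clinician. Item 18 speaks of decisions made by the program. Both points are fair, and if each method values one option the concern falls away. However, item 17 refers to percentages for each option from both methods and plans separate analyses of them. Those analyses would add little if each case were 100% on one option. Multiple values, at least from the program, are a natural reading, though not an established one.

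**The limitation is disclosed and partly covered.** The protocol says openly that kappa ignores the value, and it adds measures that use the percentages. That stands, but those measures do not count matching decisions.

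**A reader might infer that the coding flatters the program.** The documents do not support that. In the illustration, overstatement needs the program to be wrong in about 45% or more of the split cases (16.4 of 36). A coded kappa of 1.00 with no decision matching is possible, but only if clinicians also value two options, and a single delivered treatment does not suggest that.

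**A reader might also try a two-option extraction example**, with clinicians divided 50/50 or 80/20. Such an example does not match the eligible sample under inclusion criterion 2. Items 13 and 14 still speak of extraction or non-extraction, so the protocol is not consistent here. No size for extraction is claimed.

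**Space-closure percentages appear only in the literature review**, not in the Methods. They show that the meaning of the planned percentages needs stating, not that space closure is what is meant.

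**Conclusion.** The point holds conditionally. The stated coding answers a different question from the hypothesis whenever a method values more than one option in a case. In the anchorage illustration, with 36 of 90 cases split, the coded kappa stays at 0.73 while kappa on the decision can lie anywhere from 1.00 to 0.40. If the program does better than chance in such cases, the error is mostly towards understating agreement. With one valued option per method and case there is no error.

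The size rests on assumed inputs: 90 cases, balanced options, one valued option per clinician, 36 split cases, and percentages that express preference. The documents supply none of these. It should be fixed before analysis because the rule is written into the protocol and its result is graded on fixed bands. Confidence is medium because the trigger is implied and not stated.

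**What to change.** In item 17:

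1. State whether a method may value more than one option in a case, and what the percentages mean. If they are not strengths of preference, state how one decision is read from them.
2. If they express preference, define each method's decision as the single option with the highest value. Keep exact ties as a separate category, *undecided*, and report their number. Align item 18, which now treats indeterminate results as not applicable.
3. On that decision, report percent agreement with its 95% confidence interval, separately for extraction and for anchorage.
4. Report kappa on that decision for anchorage. For extraction, rely on percent agreement and give kappa only if the clinicians' decisions include enough non-extraction cases, since kappa is 0 or undefined when the reference is constant.
5. Keep the 0/1 overlap kappa as a secondary description beside the planned concordance coefficient and absolute differences.

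The cost is a few sentences in items 17 and 18 and one derived variable per decision. No new data are needed. The highest-value rule ignores how strong a preference is, but the planned value-based measures still show that.
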